9. SAMPLE SIZE CONSIDERATIONS

In view of the FMR design, there is no formal predetermined sample size. In principle, a successful FMR should include a large sample size for reliable and generalizable conclusions.³

For DCE, the required sample size (N) depends on the number of choice tasks (t), the number of alternatives (a), and the number of analysis cells (c) according to the following equation: $N > 500c/(txa)$. Where DCE studies usually require only 100 responses, the minimum sample size to show that deprescribing ATT in a certain setting is preferred over continuing the ATT with a statistical power β of 80% and a 2-sided significance level α of 0.05 is 190. This is well below the planned number of 800 observations.⁴

We will monitor the number of preregistered participants and adjust the recruitment plan based on the actual accrual.

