10. DESCRIPTION OF STUDY PROCEDURES

The study will be divided into three phases: the recruitment phase, the FMR-phase and the data analysis phase.

In the **recruitment phase**, the national coordinators of the project group will advertise the study through traditional professional networks as well as their social media channels. Information about the study will be distributed via personal communication, relevant scientific organisations and journals, and via social media. The healthcare professionals of interest will be invited to pre-register for study participation so they can be assigned a unique link to the electronic case report forms (eCRF). During the preregistration, characteristics of the pre-registrants will be checked (i.e., sex, age, profession, years of experience, the country where they are practicing, and the number of cancer patients in palliative care whom they care for on a yearly basis).

In the **FMR phase**, all preregistered participants will be asked simultaneously to complete the survey using the *Castor electronic data capture platform* within seven days.

The survey will be divided into the following sections:

- a) **General questions** regarding end-of-life care (e.g., "When do you consider a patient in end-of-life care?") and (de)prescription of antithrombotic medication to cancer patients during end-of-life care (e.g., "Have you ever considered deprescribing antithrombotic medicine?").
- b) A sequence of **choice scenarios** i.e., hypothetical scenarios that vary with regard to several characteristics (**attributes**; e.g., bleeding risk, thrombotic risk). Attributes will be further specified by varying choice levels (**attribute levels**; e.g., low or high bleeding risk), which are considered relevant for the decision on continuation or stopping antithrombotic medication in the patient population studied. In accordance with the discrete choice experiment (DCE) methodology, participants will be asked to select the healthcare intervention (i.e., either continuation or discontinuation of the antithrombotic therapy) that in their opinion would benefit the patient the most within each choice set.
- c) Participants will be asked to share **actual case decisions** they made in a maximum of three consecutive cases involving patients with active cancer, who were considered to receive end-of-life care. Fully anonymised data of the patients (sex, age category, primary tumour, tumour

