13. STATISTICAL ANALYSIS

The main analysis of the FMR will be descriptive. Results will be presented for all predefined subgroups and with corresponding 95% confidence intervals. Responses to the DCE will be used to generate preference coefficients for each level of each attribute using random parameters logit regressions, where preference weights represent the relative contribution of the attribute level to the value that participants assigned to an alternative management decision.

The attribute-level coefficients will be expressed as mean preference weights and standard deviations of the mean preference weights, each with appropriate 95% confidence interval. The relative importance of each attribute will be expressed using the within-attribute difference in preference weights as a percentage of the total difference in preference weights across all attributes. For the coefficients, the algebraic sign (positive or negative) of a coefficient reflects whether respondents feel positive or negative with regard to deprescribing. The value of a coefficient indicates the relative importance of the corresponding attribute. The statistical significance of a coefficient ($p \leq 0.05$) indicates that the respondents underline the importance of the attribute within the options in the DCE.

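### Section 13's rules for reading the DCE coefficients misstate importance (by coefficient size and by p ≤ 0.05) and leave the meaning of the sign ambiguous

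*Combined protocol and SAP*

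**What the plan says.** Section 10 has respondents choose, for each hypothetical patient, "either continuation or discontinuation of the antithrombotic therapy". Section 13 fits random parameters logit models and explains that "preference weights represent the relative contribution of the attribute level to the value that participants assigned to an alternative management decision". Means and standard deviations are to be reported, "each with appropriate 95% confidence interval". Relative importance is defined as "the within-attribute difference in preference weights as a percentage of the total difference in preference weights across all attributes".

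Three reading rules follow:
- Sign: "the algebraic sign (positive or negative) of a coefficient reflects whether respondents feel positive or negative with regard to deprescribing".
- Value: "The value of a coefficient indicates the relative importance of the corresponding attribute".
- Significance: p ≤ 0.05 "indicates that the respondents underline the importance of the attribute within the options in the DCE".

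Section 13 does not state which option is coded 1, whether dummy or effects coding is used, which levels are the references, or whether the model has a constant for deprescribing versus continuing. Section 9 sizes the DCE "to show that deprescribing ATT in a certain setting is preferred over continuing the ATT".

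**The concern.** These sentences tell the analyst how to turn coefficients into conclusions on the second objective in Section 4, the factors behind deprescribing decisions. Section 3 presents the results as a first step towards a clinical decision tool.

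The section offers three yardsticks for importance: range, single coefficient and p-value. They need not agree. Followed literally, the rules could rank an attribute by an arbitrary choice of reference level, or call a very small effect important because the sample is large. A positive coefficient could also be reported as support for deprescribing in settings where most respondents would continue.

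**Working it through.** **Inputs from the documents.** A continue/discontinue choice (Section 10); random parameters logit (Section 13); 190 and 800, two-sided 0.05, 80% power (Section 9). The Section 15.3 examples cross ECOG-PS (2 levels), thrombotic risk (2), bleeding risk (2) and medication type (3): 2 x 2 x 2 x 3 = 24 scenarios.

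**Assumptions.** All coefficients, and 8 or 24 tasks per respondent. Section 9's 190 and 800 are taken as respondents. The documents give neither task numbers nor effect sizes.

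**The plan's own figure.** The effect behind 190 is not stated. If 60% choose to stop, tested against 50%, n = (1.96 + 0.84)² x 0.6 x 0.4 / 0.1² ≈ 189, or 194 with the null variance in the first term. So 190 is compatible with a target of the form probability of stopping versus 50%. Nothing below depends on this figure.

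**1. Value rule.** Take medication weights 0 / 0.35 / 0.70 (DOAC or VKA, LMWH, antiplatelet) and a bleeding-risk weight of 0.50, dummy coded.
- DOAC/VKA as reference: the largest medication coefficient is 0.70, above 0.50.
- LMWH as reference: the coefficients are -0.35 and +0.35, below 0.50.
- Range: 0.70 either way.

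In general, for weights 0 ≤ m ≤ R with the middle level as reference, the largest absolute coefficient is max(m, R - m). The ranking against a two-level weight b reverses only when max(m, R - m) < b < R, here between 0.35 and 0.70. It does not reverse for 0 / 0.4 / 0.4 against 0.6. For two-level attributes coded alike, absolute value and range agree.

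**2. p rule.** Take a thrombotic-risk effect of -0.12, which moves the probability of deprescribing by 1.6 to 2.5 points across the illustrated scenarios. The standard errors are medians from simulated random parameters logit fits. Then z = 0.12/SE and power = Φ(z - 1.96) + Φ(-z - 1.96).

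| Respondents x tasks | SE | z | Power by formula | Significant in simulation |
|---|---|---|---|---|
| 190 x 8 | 0.142–0.152 | 0.79–0.85 | 12–13.5% | 12–13% |
| 800 x 8 | 0.065–0.069 | 1.74–1.85 | 41–45% | 45% |
| 800 x 24 | 0.036–0.037 | 3.24–3.33 | 90–92% | 91–93% |

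The preference is the same in every row; only the label changes.

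With three levels, each p-value also tests a contrast set by the reference. For weights 0 / 0.08 / 0.16, the antiplatelet contrast is 0.16 with DOAC/VKA as reference, but both contrasts are 0.08 in absolute value with LMWH as reference. Each z is therefore halved at the same SE. One joint test is the same under either reference.

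**3. Sign rule.** With stop coded 1, the log-odds of deprescribing in a scenario are the constant plus all its level weights. Hold the coefficients fixed: high bleeding risk +0.6, LMWH and antiplatelet +0.4 each, high thrombotic risk -0.12, ECOG-PS mean 0 with SD 1.5, constant SD 1. Average over the random parameters and vary only the mean constant.

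| Constant | Scenarios above 50% (of 24) | Highest probability |
|---|---|---|
| -1.5 | 0 | 42% |
| -1.0 | 0 (4 at exactly 50%) | 50% |
| -0.5 | 10 | 60% |
| 0 | 20 (2 at exactly 50%) | 70% |
| +0.5 | 24 | 78% |

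The bleeding coefficient is +0.6 throughout. At -1.5, where no scenario reaches 50%, it was positive and significant in 98–100% of simulated studies.

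**The case against.** Several points on the other side stand.

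- **Sign.** A reader might infer that the sign sentence is plainly wrong. The documents do not support that. Section 13 first defines weights as relative contributions, and with stop coded 1 a positive sign correctly means that the level pushes towards deprescribing. The fault is missing coding and loose wording. The strongest example above also needs an assumed, strongly negative constant.
- **Divided opinion.** It is tempting to say that the p rule would call an attribute on which respondents split (mean near zero, large SD) unimportant. Section 13 says only that significance indicates importance; it never states the converse. A joint test of means and the range percentage would miss such an attribute too. Only the SD shows it, and SDs are already planned, although the wording could be mistaken for a measure of precision.
- **Scope.** A reader might think the value and p faults come from the continue/discontinue format. They apply to DCE models generally.
- **Reference dependence of p.** A plain-logit calculation with 6,400 independent answers and weights 0 / 0.08 / 0.16 gives SE 0.061, z = 2.61 against 1.31, and joint chi-square 0.0256/SE² = 6.83 (p = 0.033). At the SE of about 0.08–0.09 found with random parameters, z is about 1.8–2.0 against 0.9–1.0 and the joint p about 0.14–0.21. The dependence remains, but this example is not a significant finding under the planned model.
- **Reach.** The value rule is harmless for three of the four example attributes, the range measure is already in the plan, and the 12/45/92% pattern is simply power rising with sample size. For two-level attributes a joint test has the same rejection rate. That is why the result should not be labelled importance.

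**Conclusion.** The concern holds for the value and p rules and, in a weaker form, for the sign rule.

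1. The value rule conflicts with the range-based definition two sentences before it for any attribute with three or more levels. It can reverse a ranking in some configurations, not in all.
2. The p rule is wrong: the same effect of about 2 points goes from 12% to about 92% significant as the number of answers grows.
3. The sign rule is ambiguous. No single sign establishes that deprescribing is preferred in a setting; that depends on the constant plus all level weights.

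All magnitudes are illustrative: task numbers, final attributes and true weights are not in the documents, and Section 15.3 gives examples only. The algebra behind the three points does not depend on those values. The matter is one of interpretation. It leaves the sample size unchanged, and changes the fitted model only if no constant was planned. It should be settled before analysis because it determines what the DCE is said to show.

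**What to change.** In Section 13:

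- Delete the sentence on the value of a coefficient. Keep the range percentage, with a 95% CI, as the only importance measure.
- Replace the p ≤ 0.05 sentence with one joint test of the level means per attribute, with degrees of freedom equal to the number of levels minus 1 in the final design. Describe it as evidence of an average effect, not of importance.
- Reword the sign sentence: with stop coded 1, the sign is the direction of shift towards or away from deprescribing relative to the reference level (dummy coding) or attribute mean (effects coding). State the coding and reference levels.
- Include and report a deprescribe-versus-continue constant. Base any statement that deprescribing is preferred in a setting on the model-predicted probability for that scenario, averaged over the random parameters, with a 95% CI. Report these descriptively, since the example design alone has 24 scenarios.
- Say that the reported SDs are those of the random parameters, and read them as divided opinion.

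The cost is a few reworded sentences, some post-estimation output, and a model-specification change if no constant was planned. The survey and data collection are unaffected.

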15.3 Survey: Examples of potential scenarios for the DCE

a) Variable ATT – High thrombotic risk – High bleeding risk – ECOG-PS Grade ≥ 3

Attributes	Scenario 1	Scenario 2	Scenario 3
ECOG-PS	Grade ≥ 3	Grade ≥ 3	Grade ≥ 3
Thrombotic risk	High	High	High
Bleeding risk	High	High	High
Antithrombotic medication	DOAC or VKA	LMWH (therapeutic)	Antiplatelet agent

b) Variable ATT – high thrombotic risk – low bleeding risk – ECOG-PS Grade ≥ 3

Attributes	Scenario 1	Scenario 2	Scenario 3
ECOG-PS	Grade ≥ 3	Grade ≥ 3	Grade ≥ 3
Thrombotic risk	High	High	High
Bleeding risk	Low	Low	Low
Antithrombotic medication	DOAC or VKA	LMWH (therapeutic)	Antiplatelet agent

c) Variable ATT – low thrombotic risk – high bleeding risk – ECOG-PS Grade ≥ 3

Attributes	Scenario 1	Scenario 2	Scenario 3
ECOG-PS	Grade ≥ 3	Grade ≥ 3	Grade ≥ 3
Thrombotic risk	Low	Low	Low
Bleeding risk	High	High	High
Antithrombotic medication	DOAC or VKA	LMWH (therapeutic)	Antiplatelet agent

d) Variable ATT – low thrombotic risk – low bleeding risk – ECOG-PS Grade ≥ 3

Attributes	Scenario 1	Scenario 2	Scenario 3
ECOG-PS	Grade ≥ 3	Grade ≥ 3	Grade ≥ 3
Thrombotic risk	Low	Low	Low
Bleeding risk	Low	Low	Low
Antithrombotic medication	DOAC or VKA	LMWH (therapeutic)	Antiplatelet agent

e) Variable ATT – high thrombotic risk – high bleeding risk – ECOG-PS Grade 0-2

Attributes	Scenario 1	Scenario 2	Scenario 3
ECOG-PS	Grade 0-2	Grade 0-2	Grade 0-2
Thrombotic risk	High	High	High
Bleeding risk	High	High	High
Antithrombotic medication	DOAC or VKA	LMWH (therapeutic)	Antiplatelet agent

f) Variable ATT – high thrombotic risk – low bleeding risk – ECOG-PS Grade 0-2

Attributes	Scenario 1	Scenario 2	Scenario 3
ECOG-PS	Grade 0-2	Grade 0-2	Grade 0-2
Thrombotic risk	High	High	High
Bleeding risk	Low	Low	Low
Antithrombotic medication	DOAC or VKA	LMWH (therapeutic)	Antiplatelet agent

g) Variable ATT – low thrombotic risk – high bleeding risk – ECOG-PS Grade 0-2

Attributes	Scenario 1	Scenario 2	Scenario 3
ECOG-PS	Grade 0-2	Grade 0-2	Grade 0-2
Thrombotic risk	Low	Low	Low
Bleeding risk	High	High	High
Antithrombotic medication	DOAC or VKA	LMWH (therapeutic)	Antiplatelet agent

h) Variable ATT – low thrombotic risk – low bleeding risk – ECOG-PS Grade 0-2

Attributes	Scenario 1	Scenario 2	Scenario 3
ECOG-PS	Grade 0-2	Grade 0-2	Grade 0-2
Thrombotic risk	Low	Low	Low
Bleeding risk	Low	Low	Low
Antithrombotic medication	DOAC or VKA	LMWH (therapeutic)	Antiplatelet agent

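### Section 13 reads p ≤ 0.05 for one level coefficient as importance of the whole attribute, so a three-level attribute faces about a 9% to 12% false-positive rate against 5% for a two-level one

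*Combined protocol and SAP*

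**What the plan says.** Section 13 plans to "generate preference coefficients for each level of each attribute using random parameters logit regressions". Mean weights and their standard deviations are each reported with a 95% confidence interval. Attribute importance is then addressed in two ways:

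- A relative-importance percentage compares the spread of weights within an attribute with the total over all attributes. No test is attached to it.
- A significance rule closes the section: p ≤ 0.05 for a coefficient "indicates that the respondents underline the importance of the attribute within the options in the DCE".

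Nothing is said about an attribute with several coefficients, the coding or reference level, a joint test, adjustment across attributes, or an exploratory status for the DCE p-values.

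Section 15.3 shows the attributes only as examples. ECOG-PS, thrombotic risk and bleeding risk each take two levels. Drug type takes three: "DOAC or VKA LMWH (therapeutic) Antiplatelet agent".

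**The concern.** The rule works for a two-level attribute, where one free coefficient and the attribute are the same thing. With three levels there are two free coefficients, or three tests if every level is tested. The text gives no way to combine them. The natural reading is that any significant coefficient is enough; this is an inference, because the plan does not use those words.

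On that reading:

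- Attributes with more levels get more chances at 5%, so attributes are not judged by one standard.
- Under dummy coding, the coefficients compare each drug with a reference. If only the two extreme drugs differ significantly, taking the middle one as reference can leave no significant coefficient, while taking an extreme one gives a positive verdict. The same data can support either conclusion.

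The second objective in Section 4 is to understand which factors inform deprescribing decisions, and Section 3 presents the results as a first step towards a clinical decision tool. The list of factors called important is therefore a main product of the DCE.

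**Working it through.** **The plan's own figures.** The only error rate given for attribute importance is p ≤ 0.05 per coefficient. Section 9 also gives a minimum sample size "with a statistical power β of 80% and a 2-sided significance level α of 0.05 is 190", but for a different hypothesis (that stopping is preferred over continuing in a given setting). It cannot be derived from the documents, which give neither an effect size nor values for the tasks, alternatives and analysis cells in the formula. It does not enter this check.

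**Inputs.** From Section 15.3: three two-level attributes (1 free coefficient each) and one three-level attribute (2 free coefficients), so 3 × 1 + 2 = 5. From Section 13: a threshold of 0.05, which is 1.96 on a two-sided z scale. Assumed: normal estimates, equal precision for the three drug levels, and independence between attributes.

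**Step 1. Two-level attribute with no effect.** One test at 0.05 gives 5.0%.

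**Step 2. Drug type with no effect, two dummy coefficients.** Both contrasts share the reference level, so their correlation is 0.5.

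- P(at least one |z| > 1.96) = 1 − P(|z₁| ≤ 1.96 and |z₂| ≤ 1.96) = 1 − 0.9093 = 0.0907, or 9.1%.
- If the two were independent: 1 − 0.95² = 9.75%.

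**Step 3. Drug type with no effect, every level tested.** With effects coding, the three level deviations sum to zero and are correlated at −0.5. Simulating P(any of three |z| > 1.96) gives 12.2%. All three pairwise contrasts give the same figure.

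**Step 4. Size.** 9.1/5 = 1.8 and 12.2/5 = 2.4 times nominal, for the three-level attribute only.

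**Step 5. After the fix.** A joint test on 2 degrees of freedom at 0.05 returns drug type to 5.0%. For 80% power the required noncentrality is 7.85 with 1 degree of freedom and 9.63 with 2. If the effect lies along one coefficient, the detectable effect rises by √(9.63/7.85) = 1.108, or about 11%.

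**Step 6. Across attributes (secondary).** Chance of at least one false importance claim if all four example attributes had no effect:

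| Rule | Calculation | Result |
|---|---|---|
| As written, two dummies | 1 − 0.95³ × (1 − 0.0907) | 22.0% |
| As written, every level tested | 1 − 0.95³ × (1 − 0.1219) | 24.7% |
| Joint test per attribute, no adjustment | 1 − 0.95⁴ | 18.5% |
| Joint tests, each at 0.05/4 = 0.0125 | 1 − 0.9875⁴ | 4.9% |

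With fewer null attributes the rate falls. With two null two-level attributes and no others it is 1 − 0.95² = 9.75%; with one it is 5%.

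**The case against.** The best defence is that this is a cross-sectional survey with no confirmatory hypothesis about any attribute. Section 13 does not rest importance on p-values alone, since it also gives the relative-importance percentage and confidence intervals. Section 15.3 lists examples, so the final attributes may differ. Section 10 describes the levels as ones thought relevant to the decision, which makes a complete null implausible.

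Much of this stands against a stronger reading. A reader might infer from the 22% to 25% in Step 6 that the false-positive rate for an attribute is more than four times nominal. The documents do not support that. The figure is for at least one false claim over the whole example set with every attribute null; for a single attribute the rate is 5%, or 9% to 12% with three levels. Nor does the plan promise a family-wise 5%: Section 13 applies 0.05 to one coefficient, and Section 9 applies it to another hypothesis. It would also be wrong to extend the calculation to the longer list in Section 15.2.1, which illustrates answers to two general survey questions and is not presented as the DCE attribute set.

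The defence does not remove the mismatch between test and claim. Section 13 calls the FMR analysis descriptive, not the DCE, and attaches a verdict to a threshold. The percentage has no test and the intervals are per coefficient, so neither supplies an attribute-level test.

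**Conclusion.** The point holds for attributes with more than two levels. Followed as written, the rule would call an irrelevant three-level attribute important about 9% to 12% of the time, against 5% for a two-level one. Under dummy coding its verdict can depend on an unstated reference level. The figures assume that any significant coefficient suffices and that drug levels are estimated with equal precision, and they use the example design. If the final design has only two-level attributes, this part of the problem disappears.

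The lack of control across attributes is a lesser matter of labelling. The 18.5% that remains with joint tests is illustrative, because the design is an example and a complete null is unlikely.

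**What to change.** Replace the last sentence of Section 13 with:

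> Importance of each attribute is tested by one joint Wald or likelihood-ratio test of all its mean coefficients (degrees of freedom = number of levels minus 1); p-values for single levels are exploratory and do not by themselves support a claim of attribute importance.

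This is a wording change and a few lines of code, with no change to the survey or the data. The result no longer depends on the reference level. The cost is the loss of sensitivity in Step 5: up to about 11% for the three-level attribute, and none for two-level attributes.

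Optionally, either state that the attribute p-values are not adjusted for multiplicity, or apply Holm across attributes. Labelling costs nothing. Holm costs more: at its strictest step (0.0125 with four attributes), the noncentrality needed by the 2-degree-of-freedom test is 13.31. Compared with a single-coefficient test at 0.05, the detectable effect rises by up to √(13.31/7.85) = 1.30, or about 30%. In a survey without a confirmatory attribute hypothesis, either choice is defensible if stated in advance.
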